3. suspected or proven allergy to tPA or DNase
4. chronic lung disease or other chronic illnesses (e.g. immunodeficiency or neurologic impairment)
5. child has already undergone a drainage procedure (e.g. chest drain or VATS).
6. recent administration of an investigational drug (within previous 30 days)
7. pregnancy
8. breastfeeding

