Clinical Samples at the Hospital for Sick Children: At the SickKids site only, consent will be obtained to store samples of chest tube drainage from subjects. These samples will be used for future testing to determine the microbiological cause of empyema.

Concomitant Medication: Patients in either arm will not receive any intrapleural drug other than directed from this study.

Criteria for discontinuing study interventions: Patients who develop anaphylaxis or serious bleeding (requiring a blood transfusion or resulting in a hemoglobin drop of ≥ 20 g/L) while receiving study interventions will not receive further study drugs. Patients whose chest drains is displaced will only be replaced if clinically indicated for pleural fluid drainage and not for study drug administration alone. Outcomes for all patients who do not received the full study interventions will be analyzed in the group they were assigned to.

Standard care: In keeping with a pragmatic-type trial design, all children will receive standard care for this condition including supportive care, laboratory investigations, imaging, antibiotics, chest drain care and removal and discharge as outlined in the standard care guidelines. Although some variability is expected in care among treating physicians, rigorous randomization and blinding should ensure that confounders are equally distributed between groups. A detailed care map will be adapted from the existing clinical practice guideline co-authored by team investigators (EC and SM) together with the Canadian Pediatric Society. Specific elements in the care plan include:

- a) *Antimicrobial management* - Patients in both treatment arms will receive standard therapy for pleural empyema in children as directed by the responsible physician and standardized guidelines. All participating hospitals currently recommend a 2nd or 3rd generation cephalosporin (cefuroxime or ceftriaxone or cefotaxime) as the empiric antimicrobial therapy with possible addition of clindamycin or vancomycin if *S. Aureus* is a suspected etiology. It is expected that antibiotic regimens will be tailored in line with local microbiology advice.
- b) *Drain insertion* - Chest drains will be placed using an image guided percutaneous technique by interventional radiologists or by a surgeon using a standardized technique under anesthesia agreed upon by all sites. The recommended size of catheter drain used will be an 8 or 10 French pigtail catheter.

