Recruitment: All study patients will be initially identified by research assistants who will review both (a) all new admissions to the relevant inpatient units in each study centre twice daily; and, (b) all referrals for chest drainage insertion at each centre. It is anticipated that most drains at both sites will be inserted by interventional radiologists, although a minority may be inserted by general surgeons. Physicians and radiologists/surgeons will also be asked to notify the site research assistant and/or site investigator of children admitted with pleural empyema who may be eligible for the study. Patients will be approached, eligibility criteria confirmed, consent obtained, and enrolled after the decision to refer for chest drainage but before chest drain insertion occurs.

Randomization – Sequence generation, allocation concealment and implementation: After informed consent is obtained, patients will be randomized into treatment groups using a random allocation sequence facilitated by the Applied Health Research Centre (AHRC), which will be the coordination and management centre for the trial and administered by the hospital research pharmacies. Randomization will be stratified by centre. Blocking will be used to ensure that the two comparison groups are about the same size throughout the trial for each center and for the trial as a whole (about 49 per group). An allocation ratio of 1:1 with random block size will be used within each stratum (centre). This will help to ensure that clinicians, investigators, or outcome assessors will not decipher the block size. A computer-based pseudo-random number generator will be used to create treatment allocation tables for each study center. After patient eligibility has been confirmed and consent obtained and just as the patient leaves the inpatient unit to the radiology suite or operating room for chest drain insertion, the site investigator, or his/her delegate, will assign the patient a unique study identification (ID)

number in sequential order. The study ID will correspond with the randomization table held in the research pharmacy for dispensing blinded DNase or placebo. The biostatistician will maintain a secure master list of the randomization codes and the assigned treatments will be checked against the master list at the end of the study.

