Blinding: Patients, their parents or other caregivers, site investigators, research assistants and coordinators, treating physicians (pediatricians, radiologists, and interventional radiologists or surgeons), treating nurses, and data managers will be blinded to the treatment allocation. Group allocation will be concealed until the final data analysis is performed. Intervention drugs will be blinded by the research pharmacy. Both arms will be constituted by the research pharmacies in clear liquids in a polyethylene container⁴² in a manner such that both are identical (packaging, colour, volume, texture, and odour) to ensure blinding. After obtaining the treatment number from the central randomization centre, the study pharmacist will retrieve the corresponding vial and one of its treatment number labels will be attached to the patient's case report form (CRF).

Unblinding Procedures: We do not anticipate any circumstances that would require unblinding as knowledge of study arm is not anticipated to affect any treatments for patients.

Data collection methods: Data collection for outcome measures will be mainly collected in hospital by the Research Assistant (RA). At baseline, the following data will be obtained: age, sex, duration of antibiotic treatment prior to chest drainage insertion (days), duration of fever prior to chest drain insertion (days), hypoxia in room air (oxygen saturations less than 92% in room air prior to intervention), microbiologic identification of causative agent (blood culture results, throat swab, pleural fluid culture, pleural fluid PCR), ultrasound of chest: pleural effusion size >10 mm <10 mm, stage of empyema on ultrasound of chest: Stage 1: anechoic nonseptated fluid; Stage 2: echoic fluid without septation; and Stage 3: septated fluid and Stage 4: septations with solid appearing components comprising more than one third of the effusion.⁵³ All ultrasounds will be reviewed by a blinded study radiologist (BC). In addition, patients will receive a follow-up phone call from the RA at 3 months enquiring about any possible readmissions and ongoing symptoms of fever, shortness of breath and/or exercise intolerance.

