Secondary outcomes and exploratory outcome: For the secondary and exploratory outcomes that are continuous variables (e.g. duration of drain insertion, hospital stay after intervention to meeting discharge criteria, duration of fever after the intervention, amount of hemithorax occupied by pleural effusion in radiographs) the difference between the two means with the 95% confidence intervals will be presented. The student's t test will be used to detect a difference between the treatment groups. Dichotomous outcomes (serious bleeding, need for further interventions, need for ventilatory support, mortality) will be described as the absolute number and proportion. A Fisher's exact test will be used to detect a significant ($p < 0.05$) difference between the two treatment arms. The treatment effect will also be presented as the relative risk with 95% confidence intervals. These analyses will be viewed as hypothesis generating, and therefore, no correction for multiple testing is planned.

Data Monitoring and Safety: Data monitoring will be conducted with a Data Monitoring Committee (DMC) composed of a pediatric hospitalist, a respiratory physician and an interventional radiologist. The DMC will be completely independent of the investigators, and will be provided with clinical information from the trial case report forms for death, surgical events and adverse events, including those that were described in the adult DNase trial (hemoptysis, gastrointestinal bleeding, chest pain, nausea, transient confusion and rash). The DMC will be able to request additional information from clinicians.

Adverse Event Reporting: All serious unexpected adverse events will be reported to the REB; as per SickKids REB guidelines. All serious adverse drug reactions to the study medication will be reported to Health Canada within 15 calendar days or for death or life-threatening events, within 7 calendar days. In the latter case, a follow-up report will be filed within 8 calendar days. Adverse reactions will be managed according to the standard clinical management practices. All adverse events and adverse reactions will also be reported to the PI within 24 hours.

[figure not shown]
Quality Assurance: This project will be monitored by The Applied Health Research Centre (AHRC) during the data collection phase of the project. The aim is to ensure that all researchers are maintaining

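### No individual code-break is described, so after a serious reaction neither the child's allergy record nor the safety report can establish whether DNase was given

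*Combined protocol and SAP*

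**What the plan says.** Unblinding Procedures consists of one sentence: "We do not anticipate any circumstances that would require unblinding as knowledge of study arm is not anticipated to affect any treatments for patients". The Blinding section just above it lists families, site investigators, research staff, treating physicians, nurses and data managers as blinded, and adds: "Group allocation will be concealed until the final data analysis is performed". No exception is given.

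Other sections of the same document bear on this:

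- Criteria for discontinuing study interventions: the rule concerns "Patients who develop anaphylaxis or serious bleeding"; its consequence, the same in both arms, is that those affected "while receiving study interventions will not receive further study drugs".
- Exclusion criterion 3: "suspected or proven allergy to tPA or DNase".
- Adverse Event Reporting: "All serious adverse drug reactions to the study medication will be reported to Health Canada within 15 calendar days". Where the event is fatal or threatens life, the limit is shortened to 7 days.
- Randomization: "The study ID will correspond with the randomization table held in the research pharmacy". The biostatistician also keeps a master list. The only uses named for these lists are dispensing and a check at the end of the study.

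**The concern.** The reason given for expecting no unblinding is that the arm would not change treatment. That leaves out two other uses of the information. One is the child's own record: a child who has an anaphylactic reaction goes home with a question about which drug is suspect, and the eligibility criteria themselves treat allergy to DNase as something that matters. The other is the expedited report, which concerns a reaction to the study medication. A child given tPA then saline cannot have reacted to DNase.

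If the plan is followed as written, the DNase exposure of a reacting child stays unknown to the family, the treating team and the blinded site staff until the trial ends.

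**Working it through.** The point rests on reading the sections together. Arithmetic only sets its scale.

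**Step 1: number of children.** Inputs from Sample size: SD 2.9 days, difference 2 days, two-sided 0.05, power 90%. The exact two-sample t calculation gives 45.17, rounded up to the plan's 46 per group. The 5% allowance gives 46 × 1.05 = 48.3 or 46 / 0.95 = 48.4, both rounded up to the plan's 49. The total is 2 × 49 = 98, of whom 49 are assigned DNase and 49 saline, all with tPA. Nothing below changes these figures.

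**Step 2: what does and does not depend on the arm.**

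- *Stopping study drug after anaphylaxis or serious bleeding:* the same rule in both arms, so no code is needed.
- *Clinical handling of the reaction:* Adverse Event Reporting refers to standard practice and does not mention the arm.
- *Whether the child was exposed to DNase:* depends on the arm once the first blinded syringe has been given. Under Interventions, tPA is clamped for one hour and drained for one hour before that syringe. A reaction in those first two hours came before any DNase in either arm; for later reactions the code is needed.
- *Whether a reported reaction can be a reaction to DNase:* depends on the arm in the same way.

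**Step 3: is there a route to the code?** The pharmacy prepares the syringes and holds the table, so the information exists at each site. No section says who may ask for it, who may release it, how a break is recorded, or who stays blinded. Adverse Event Reporting does not say whether the arm accompanies an expedited report. Data Monitoring and Safety describes case-report information going to the committee and does not mention allocation.

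**Step 4: how often.** The documents give no anaphylaxis rate. For an assumed per-child rate p, the chance of at least one case among 98 is 1 − (1 − p)^98:

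- p = 0.1%: 1 − 0.999^98 = 9%
- p = 0.5%: 1 − 0.995^98 = 39%
- p = 1%: 1 − 0.99^98 = 63%

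These rates are illustrative only. Even at 1%, the expected number of cases is 98 × 0.01 = 0.98.

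**The case against.** The best defence is that the sentence is accurate within its own terms. It speaks of treatment, and no section describes a treatment that differs by arm. Exclusion criterion 3 covers suspected as well as proven allergy, so a reacting child could be recorded as possibly allergic to both drugs without the code. The code would not settle cause either, since every child is also on antibiotics. And the Background describes nebulized DNase as well tolerated and reports no excess of adverse events with the combination in adults.

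Much of this stands, and it disposes of several stronger readings that a reader might infer:

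- *That the plan forbids unblinding.* It does not. The sentence is a forecast, and access to the pharmacy table is undescribed, not barred.
- *That the sections contradict one another on treatment.* They do not. The gap is an omission concerning exposure.
- *That serious bleeding makes the same case.* It does so only weakly. Every child receives tPA, and the Fibrinolytics section says that bleeding from drain insertion is hard to separate from bleeding due to the drug. The 2% bleeding prevalence quoted there implies 98 × 0.02 = 1.96 cases and a 1 − 0.98^98 = 86% chance of at least one. But it covers any hemoglobin drop, which is wider than the trial's definition, and says nothing about anaphylaxis.
- *That half of all reacting children never had DNase.* Half of those randomized is correct. If DNase multiplies the reaction risk by r, the unexposed share of reactors is 1/(1 + r): 50% at r = 1, 33% at r = 2, 25% at r = 3. The figure of one half assumes that DNase does not change the risk.
- *That expedited reports must be unblinded.* The documents do not say so; they are silent on whether the arm is disclosed.

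What the defence does not answer is the loss of exposure information. Recording every reacting child as possibly DNase-allergic would label children who received saline, and a report that cannot state the exposure is less informative than it could easily be.

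**Conclusion.** The point holds in a limited form. The plan foresees anaphylaxis, treats DNase allergy as relevant and requires reports within 7 or 15 days, yet provides no way to learn one child's allocation before the final analysis. For a reaction after the first blinded syringe, neither the allergy record nor the report can establish DNase exposure.

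This is a safety and reporting gap, probably touching few or no children; the number rests on an anaphylaxis rate that the documents do not supply. It does not threaten the primary comparison. One or two code-breaks among 98 (an assumption) would be 1% to 2% of the sample, and the Statistical Analysis section already keeps children with incomplete study drug in their assigned group.

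**What to change.** Reconcile the exclusion criteria, the discontinuation criteria, Blinding, Unblinding Procedures and Adverse Event Reporting by replacing the one-sentence statement with an individual-patient emergency code-break. It should run through the research pharmacy, which holds the randomization table, or from the biostatistician's master list. The text should state:

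- who may request the code, who releases it, and that access is available at all hours;
- that all other staff and the outcome assessors stay blinded where possible;
- that each break is logged with date, reason and recipients, and reported by arm at the end of the trial;
- whether expedited reports carry the arm and, if so, who prepares them;
- that a child whose code is broken stays in the intention-to-treat analysis.

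The sentence on concealment until the final analysis needs a matching exception. The cost is protocol wording and a pharmacy procedure, with no change to sample size, treatment or primary analysis. The downside is small: the few affected children, and possibly their treating clinicians, become unblinded. Because those clinicians also decide on drain removal and discharge, the log should record whether the break came before discharge.

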Sample Size: A sample size of 92 (46 per group) will have the power to detect a 2 day difference in length of stay between the groups. While we do not anticipate any post-randomization ineligibility, for example from misdiagnosis, we will increase the sample size by 5% to account for this possibility (total of 49 patients per group). It is anticipated that over the study period, 180 children will be admitted to the five centres who meet eligibility criteria.

Analysis: Student’s t-test will assess differences in the primary outcome between groups.

FEASIBILITY

The investigators are clinical experts with a strong track record in outcomes research in pediatric empyema and methodological experts in clinical trials.

COMPLICATED PNEUMONIA (PLEURAL EMPYEMA) IN CHILDREN

Pneumonia is one of the most common reasons for hospitalization in childhood,¹ and accounts for more inpatient resource utilization (cost) than any other pediatric diagnosis outside of the newborn period.² Up to 50% of children hospitalized with pneumonia have an associated parapneumonic effusion.³ Most of these effusions are small and uncomplicated and will resolve with antimicrobial treatment of the underlying infection, but in some cases, a complicated effusion can develop characterized by enlargement leading to respiratory compromise and/or extensive loculations. Such effusions, commonly referred to as pleural empyema, characteristically lead to substantial morbidity including respiratory distress, pain, and prolonged hospitalization leading to child school loss, parental work loss and stress on families. These children generally do not respond to antibiotic therapy alone and require management with a drainage procedure. In recent years, there has been a dramatic increase noted in the incidence of pediatric pleural empyema in multiple countries.⁴⁻⁹ A review of Canadian data (excluding Quebec and Manitoba) found that there are now over 1,400 new cases each year.¹⁰ Hospitalization data from the United States seems to suggest that this growth has been most apparent in young children, aged 2-4 years,¹¹ with Canadian data documenting a recent increase in incidence rates by over 450% in those aged 1-4 years.¹⁰ Although the exact cause of this epidemiologic change is somewhat unclear, postulated causes include pneumococcal serotype replacement and increasing antibiotic resistance.¹²

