Sample size: The primary endpoint is time to hospital discharge after intervention. The mean time to hospital discharge after chest tube insertion and fibrinolytics varies. Published studies with treatment arms that have included chest drain with fibrinolytics as the primary mode of insertion reported hospital days after the intervention from 6 to 15 days.^{23,24} Hospital length of stay tends to be shorter in published RCTs compared with observational studies of empyema, and the most recently published RCT using an identical tPA dosing regimen to that which we are proposing described a mean (SD) stay of 6.8 (2.9) days.³¹ The desired power for the current proposal is 90% to detect a difference of 2 days in the mean time to hospital discharge between the treatment arms. Based on discussions with clinical experts in the field, hospital administrators and parents of children with pleural empyema, it is believed that a 2 day difference between treatment groups is a minimal clinically meaningful difference, and this has been used in previous empyema trials.²⁷ The adult DNase trial found about a 50% difference in length of stay between treatment and placebo groups.⁴²

Sample size was thus calculated assuming a type 1 error rate of 0.05 (2 sided), power (1-β) of 90%, a standard deviation of 2.9 days for each group to detect a difference of 2 days to be 46 per group. Calculations were performed based on a t test of independent groups. While we do not anticipate any post-randomization ineligibility, for example from misdiagnosis, we will increase the sample size by 5% to account for this possibility (total of 49 patients per group). There will be no other adjustment to the sample size requirements due to loss to follow-up for the primary outcome as the primary outcome is assessed in hospital where the research coordinator will be able to ensure complete data collection.

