Primary outcome: Data will be analyzed according to intention to treat principles for the primary outcome (e.g. patients who do not receive all three doses of study drug will be analyzed in the group they were assigned to). Exceptions to this principle will only include any patient who dies in hospital and will be excluded from the analysis of time to hospital discharge. Given that the primary outcome and other acute secondary outcomes are obtained during hospitalization, it is anticipated that there will be no missing data for these outcomes with the possible, but unlikely exception of in-hospital death, which is rare in childhood empyema. For the follow up outcomes at 3 months, the proportion of patients who follow up will be presented for each treatment arm, and patients who are lost to follow up will be stated but omitted from the analysis. The primary outcome, time (in days) to hospital discharge, will be described as the difference between the two means with the 95% confidence intervals. The student's t-test (independent two sample test assuming equal group size and variance), will be used to detect a difference between the two treatment groups. If the resulting data is inappropriate for a t-test (increasing variance with the mean is the biggest concern since the test is quite robust to non-normality in the population), a suitable transformation or non-parametric test may be used. If feasible, a secondary analysis of the primary outcome will analyze time to discharge, treating death as a competing risk, using methods for survival data. Since randomization is stratified between five centres, the analysis will adjust for this stratification by including centre as a covariate in a multiple linear regression model, to obtain adjusted treatment effects. Additionally, a treatment by centre interaction will be tested to see if the treatment effect differs between centres. Subgroup analyses will also be conducted to explore any potential differences in outcomes by age or sex.

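### Randomization is stratified by centre, but the default primary test ignores centre and the planned centre-adjusted regression is not ranked against it; one centre-adjusted model in untransformed days would settle this, and the unnamed fallback test as well

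*Combined protocol and SAP*

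**What the plan says.** The Randomization section states: "Randomization will be stratified by centre". There are five centres, with 1:1 allocation in random blocks within each.

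Three places make the unadjusted t-test the default. The summary's Analysis line says a Student "t-test will assess differences in the primary outcome between groups". The Sample size section says: "Calculations were performed based on a t test of independent groups". Under Statistical Analysis, Primary outcome, the t-test "will be used to detect a difference between the two treatment groups", and the outcome "will be described as the difference between the two means with the 95% confidence intervals".

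The same paragraph then adds two things:

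- If the data turn out unsuitable for a t-test, "a suitable transformation or non-parametric test may be used". The reason given is that "increasing variance with the mean is the biggest concern since the test is quite robust to non-normality in the population". No diagnostic, cut-off, transformation or replacement test is named.
- Because of the stratification, "the analysis will adjust for this stratification by including centre as a covariate in a multiple linear regression model". This model is not called primary, secondary or sensitivity. The competing-risk analysis in the same paragraph is explicitly called secondary.

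**The concern.** Stratifying by centre balances the arms within centres, which removes between-centre variation from the true error of the treatment difference. An unadjusted t-test still counts that variation as noise. Its standard error is then too large, its p-value too cautious and its interval too wide.

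The plan will produce both the unadjusted and the adjusted result in every case. If they fall on opposite sides of 0.05, no rule says which one counts.

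The open fallback is a separate and smaller matter. A log-scale or rank test does not test the difference in mean days, which is the quantity on which the trial was sized.

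**Working it through.** **1. The plan's own figure.** Inputs from the Sample size section: difference 2 days, SD 2.9, two-sided 0.05, power 90%. The exact t-test solution is 45.17, rounded up to 46 per group. Inflation by 5% gives 46 × 1.05 = 48.3, so 49. Power is 90.5% at 46 and 92.2% at 49 per group. The stated numbers reproduce.

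**2. Effect of ignoring centre, by formula.** Let R² be the share of variance explained by centre. The documents give none, so 0, 5, 10 and 20% are assumed.

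- Unadjusted standard error: 2.9 × √(2/49) = 0.586 days. With t(96 df) = 1.985, the interval width is 2 × 1.985 × 0.586 = 2.33 days.
- True standard error with arms balanced within centre: about 0.586 × √(1 − R²). The t-test's null rejection is therefore about P(|t₉₆| > 1.985/√(1 − R²)).
- The adjusted model has 98 − 6 = 92 df, t = 1.986 and width 2 × 1.986 × 0.586 × √(1 − R²).

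| Assumed R² | 1.985/√(1 − R²) | t-test null rejection | Adjusted width (days) | 2.33 / adjusted width | Adjusted power at 2 days |
|---|---|---|---|---|---|
| 0 | 1.985 | 5.0% | 2.33 | 1.00 | 92.2% |
| 5% | 2.037 | 4.4% | 2.27 | 1.03 | 93.4% |
| 10% | 2.092 | 3.9% | 2.21 | 1.05 | 94.5% |
| 20% | 2.219 | 2.9% | 2.08 | 1.12 | 96.5% |

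**3. The same by simulation.** 98 patients, five centres of assumed equal or unequal size, total SD 2.9, mostly gamma stays (assumed). The adjusted model uses HC2 standard errors. Ranges cover repeated runs.

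| Assumed R² | Null rejection: t-test / adjusted | Mean CI width in days: t-test / adjusted | Power at 2 days: t-test / adjusted |
|---|---|---|---|
| 5% | 4.3–4.6% / 4.8–5.1% | 2.32 / 2.26–2.27 | 92.6% / 93.1–93.3% |
| 10% | 3.8–4.1% / 4.8–5.0% | 2.32 / 2.20 | 92.3–93.2% / 93.8–94.6% |
| 20% | 2.8–3.0% / 4.8–5.1% | 2.32 / 2.07–2.08 | 94.0–94.7% / 96.3–96.5% |

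Width ratios run from 2.32/2.27 = 1.02 to 2.32/2.07 = 1.12. At R² = 0, power is 92.0% unadjusted against 91.9% adjusted. At R² of 5/10/20% the two verdicts differ in 0.7–0.9/1.1–1.3/2.1–2.2% of null trials and in 1.0/1.5–1.7/2.3–2.5% of trials with a 2-day effect.

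**4. The fallback.** 49 per arm, mean 6.8 and SD 2.9 (Sample size section), gamma or lognormal stays (assumed). The trigger is assumed to be a Brown-Forsythe variance test at p < 0.05, and the replacement a log t-test or Mann-Whitney test.

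- Trigger fires and the verdict changes: 0.4–0.6% of trials with no effect; 0.1–0.7% at 2 days with SD proportional to the mean; 0.4–0.6% at 2 days with equal SDs; 1.3–2.6% at 1 day with SD proportional to the mean.
- Type I error of the conditional switch when the arms do not differ: 3.8–4.7% over five assumed triggers.
- Equal means, variance ratio 2: the t-test holds at 5.1–5.2%. A log test used throughout rejects in 8.4–13.4% and a rank test in 7.1–10.9%, because they test a different hypothesis. The conditional switch gives 4.2–6.1% with this trigger and up to 10.4% with the loosest of the five.

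So with 1:1 arms, the unequal variance that the plan worries about does not itself call for leaving the t-test.

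**The case against.** The natural reading is that the t-test is primary and the regression supportive: it is introduced later, to give adjusted effects, alongside the interaction test. That is fair. What is missing is a label, and a conservative test creates no false claims. But this reading settles on the less precise of two analyses already planned.

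The Study Setting section describes similar prescribing, mostly the same drain technique and pathways to standardize care, so the centre effect may be small. That also stands; at R² = 0 the gain is nil. The cost is then nil too, to within about 0.1 point of power.

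Keeping days untransformed is not entirely free. If stays are skewed with equal SDs, a log test would have about 98–99% power at 2 days, against 91–92% for the t-test. That is a real but small downside, since the untransformed model still meets the planned 90%.

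Stronger readings of the fallback are tempting but not supported:

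- A reader might infer that it invites picking the best of three tests, with type I error of 6.8–6.9%. The plan makes replacement conditional on unsuitable data and does not allow free choice. With no effect, nearly all changed verdicts under the assumed trigger remove false positives.
- A reader might infer that a mean-difference interval would be printed beside a contradictory log or rank p-value. The text describes the effect that way for the default analysis and does not say it would be kept after a switch.
- Looser assumed triggers raise the share of changed verdicts at 2 days with equal SDs to 5.6%. That figure consists entirely of correct detections gained, so it is not a measure of harm.

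The Blinding section conceals allocation until the final analysis, which limits opportunistic choice during the trial. It does not say that the test is fixed before unblinding.

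**Conclusion.** The point holds as a precision gain at almost no cost, not as an error that threatens validity. The default primary test ignores the stratification factor, and the regression that respects it has no stated rank. With centre explaining 5–20% of variance, the t-test is conservative (about 2.8–4.6% instead of 5%), its interval is about 2–12% wider than the adjusted one, and the two verdicts differ in roughly 1–2.5% of trials. These sizes depend on the assumed R², centre sizes and distribution. The missing rank rests on the text alone.

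The open fallback is a minor loose end, worth closing in the same edit because a replacement test would not address the mean difference in days. Nothing here suggests that the trial is underpowered: the sample size and 90% power are correct.

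**What to change.** In Statistical Analysis, Primary outcome, replace the t-test, fallback and centre-covariate sentences with wording to this effect:

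> The primary analysis is a linear regression of untransformed days to discharge on treatment and centre, with heteroscedasticity-robust (HC2) standard errors. The adjusted mean difference, its 95% confidence interval and its two-sided p-value are the primary result. The unadjusted t-test and a log-scale or rank test are reported as sensitivity analyses only.

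State the reference distribution for the robust test (for example, t on the residual degrees of freedom), and update the summary's Analysis line to match. The robust standard errors cover the unequal-variance concern without a data-driven switch.

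The cost is wording only: no new data, no change to the sample size and no covariates beyond centre. The price is about 0.1 point of power if centre explains nothing, plus the log-test power given up in the skewed, equal-SD case.
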